**Table 2-2 Visit windows for the post-treatment safety follow-up period**

Analysis visit	Time point	Scheduled visit day (study days)	Visit window (study days)
Safety FU visit 1	EOS + 3 months	458	428 to 503
Safety FU visit 2	EOS + 6 months	549	504 to 594
Safety FU visit 3	EOS + 9 months	640	595 to 685
Safety FU visit n (n>3)	EOS + n*3 months	640+91*(n-3)	595+91*(n-3) to 685+91*(n-3)

#### 2.4.2.1 Vital signs, laboratory, biomarker and questionnaire

Chemistry, Hematology, Sample for CD+19 B-cells & CD20+CD3+ T-cells, LBCAT=Immunophenotyping, Total IgG and IgM levels, Urinalysis, serology (only measured at baseline visit), vital signs, [REDACTED], and questionnaires ([REDACTED]) are to be carried out at Screening, Baseline Day 1, Month 1, Month 6, Month 12 (EOS) and any unplanned visits. These are measured at EOS + 3 Months, EOS + 6 Months, and if required, at every 3 months after the 6 Month follow up for the patients requiring prolonged B-cell plasma level monitoring. Weight is not measured at unplanned visits, and height is only measured at the baseline visit. C-SSRS, TSQM-9, [REDACTED] are not measured at post-treatment Safety FU, [REDACTED].

Based on this criteria, for the above information, the visit windows are shown in [Table 2-3](#). The window is based on the visit day for the scheduled visit +/- the additional days based on the half mark between the next/previous scheduled visit.

**Table 2-3 Visit windows for vital signs, laboratory, biomarker and questionnaire**

Analysis Visit	Time Point	Scheduled visit day (study days)	Visit window (study days)
Baseline	Day 1	1	-28 to 1
Visit 4	Month 1	31	2 to 107
Visit 9	Month 6	184	108 to 275
(EOS) Visit 15	Month 12	366	276 to 427
Safety FU visit 1	EOS + 3 months	458	428 to 503
Safety FU visit 2	EOS + 6 months	549	504 to 594
Safety FU visit n (n>2)	EOS + n*3 months	549+91*(n-2)	504+91*(n-2) to 594+91*(n-2)

#### **2.4.2.2 Morphology**

Morphology i.e. MRI assessments are to be carried out at Screening, Month 6, and Month 12 (EOS). However, the final assessment of subjects who discontinue early is recorded as Month 12 (EOS). Based on this criteria, the visit windows for morphology are shown in [Table 2-4](#).

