2.2 Secondary estimands

Not applicable

3 Study design

This is a single-arm, multi-center, prospective, study in approximately 100 participants with relapsing multiple sclerosis who have been previously treated with aCD20 mAb therapy and have received at least 2 consecutive courses of intravenously administered ocrelizumab or rituximab every 6 months and the last dose is within 4 to 9 months before Baseline/Day 1. In this study, participants may enroll only if discontinuing aCD20 therapy for reasons other than lack of efficacy or due to certain treatment-emergent adverse events. Reasons for switching may include but are not limited to physician/participant preference, access to commercial drug (e.g. insurance coverage issues) or for other logistical reasons (such as geographical relocation, travel, etc.) A total of approximately 100 eligible participants will receive open label ofatumumab 20 mg subcutaneous once monthly for 12 months following initial loading regimen of 20 mg subcutaneous doses on Days 1, 7 and 14.

Assessments will be done per the assessment schedules ([Table 8-1](#) and [Table 8-2](#)).

For participants who discontinue study treatment prematurely for any reason before the end of the treatment phase, an End of Study visit must be performed within 7 days of study discontinuation.

Upon completing the study, participants may continue ofatumumab therapy on commercial drug.

Safety follow-up:

[figure not shown]
- The Safety follow-up (FU) period will be applicable for the following participants:
 - participants who complete the Treatment period on the study drug and do not continue on any MS DMT.
 - participants who prematurely discontinue study drug and do not continue on any MS DMT.
- All Safety FU visits must be scheduled relative to the End of Study (EOS) Visit.

Participants that do not continue into the ofatumumab commercial patient services hub within one month of the EOS Visit or that do not switch to another therapy, must continue into the safety FU phase, consisting of every 3 month visits including B cell monitoring until they are able to start on commercial ofatumumab or until they switch to another therapy or until their B cells are repleted defined as a B cell concentration greater than the individual participant's baseline value prior to starting the IV anti-CD20 mAb or greater than the lower limit of normal. All participants will have a safety follow-up phone call at 30 days post study.

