	
X = assessment to be recorded in the clinical database or received electronically from a vendor S = assessment to be recorded in the source documentation only
 
 1. Visit structure given for internal programming purpose only. 2. All baseline assessments are to be performed prior to dispensing/dosing study drug. 3. ECG to be performed pre-dose on BSL (Day 1). 4. Enrollment (Day1/BSL) first dose (usually expected on the same day). If first dose occurs on a different day after enrollment, the day of the first dose should be considered as Day 1. 5. EOS visit will be required for all participants (participants who permanently discontinue study drug and participants who complete the study). 6. MS history including number of relapses in previous year and number of relapses in previous two years, all infusion reactions on previous therapy and the reason for switching from previous intravenous aCD20 must be captured. 7. Participant training on study requirements including study drug administration using the autoinjector, ePRO, functionality and use. 8. Remote contact with participants by site staff around the time of administration of ofatumumab self/home-injection. The contact should query about any new or worsening symptoms warranting an unscheduled visit, MS relapse compliance with study treatment, injection reactions, compliance with contraception requirements (when applicable). Method of contact can be via telephone, email or text message depending on the preference of each participant. 																	

Period ¹	Screening / BSL		Treatment Period													End of Treatment /Study	Follow-up	Unplanned
Visit Name	Screening	BSL V1	V2	V3	V4	V5	V6	V7	V8	V9	V10	V11	V12	V13	V14	EOT/EOS V15 ⁵	Safety	Unscheduled Visit
Visit Day (D)/Month (M)	-28 Days	D1	D7	D14	M1	M2	M3	M4	M5	M6	M7	M8	M9	M10	M11	M12	30-Day Tel.	UPV
Visit Window Days (d)			±1d	±1d	±3d	±3d	±3d	±3d	±3d	±3d	±3d	±3d	±3d	±3d	±3d	±3d	±7d	

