
9. Restrictions may apply to MRI concerning steroid use, please refer to Section 8.3.4. Scans of the brain and cervical spine are needed.
 
10. Screening MRI should be completed once all other screening eligibility assessments have been completed and confirmed to meet eligibility criteria.
 
11. MRI scan at the EOS/EOT visit is required.
 
12. All assessments to be completed prior to baseline visit/first study drug administration.
 
13. Vital signs should be obtained 30-60(+/- 10min) minutes before the subcutaneous injection (study drug). If premedication is required, the vital signs should be taken prior to premedication administration. At the baseline visit only, systolic and diastolic blood pressure should be measured 3 times.
 
14. If the scheduled visit coincides with the day that study drug administration is scheduled, the participant should be instructed not to administer the injection before coming to the site so that the safety assessments can be completed prior to study drug administration unless the scheduled visit is outside of the 3 day window for drug administration.
 
[REDACTED]
 
16. Labs must be drawn to allow adequate time for results to be obtained before first study drug administration to ensure participant's eligibility.
 
17. Participant's contraception status must be reviewed and documented to ensure method of contraception continues to be appropriate per protocol requirement for highly effective contraception. Pregnancy test is conducted on female participants only. Urine pregnancy tests will be conducted at all scheduled visits as indicated in Table 8-1. The participant must contact the Investigator immediately in the case of a positive test for confirmatory testing at the Investigator's discretion.
 
[REDACTED]
 
[REDACTED]
 
21. Urine dipstick: If positive send full urinalysis to central laboratory.
 
22. Site staff must observe the participant /caregiver administer study drug at Mo. 1 and Mo. 6 after all assessments have been completed with the exception of the MRI at Mo. 6.
 
24. Additional unplanned ECGs may be performed at the Investigator's discretion if clinically indicated.
 
25. Historical IgM and IgG results if available from pre-baseline of IV anti-CD20 treatment (one result pre-infusion) and then any testing done following IV anti-CD20 initiation. This should be recorded once for all participants enrolled or completed and may be collected at any visit.
																		

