### **2.4.2 Visit windows**

Visit windows will be used for the data that is summarized by visit; they are based on the study evaluation schedule and comprise a set of days around the nominal visit day. For any assessment, there are the protocol defined scheduled visits around which visit windows are created to cover the complete range of days within the study.

The visit windows for the on-treatment period are shown in [Table 2-1](#). In this table, the days are counted since the first dose of study treatment (study days) for safety and efficacy assessments. These windows apply to measurements taken at every visit. For assessments collected less often different visit windows will be applied as detailed below. Similarly, visit windows for the post-treatment safety follow-up period are shown in [Table 2-2](#). Unless specified otherwise these windows will be applied for all assessments.

When visit windows are used, all visits will be re-aligned, i.e., they will be mapped into one of the visit windows. E.g., if the Visit 4 visit of a participant is delayed and occurs on Day 62 instead of on Day 30, say, it will be re-aligned to visit window Visit 5. In the case of major deviations from the visit schedule, or due to unscheduled visits, several assessments of a participant may fall in a particular visit window (either scheduled or unscheduled). Statistical approaches to handle multiple assessments in a given visit window are specified below.

Tables displaying summary statistics “by visit” will also use the term visit-window as column header; this is to remind the reviewer that multiple assessments of a patient might be summarized.

As a rule, the following steps are followed to determine the cut-offs for post-baseline time windows:

- Transform all scheduled assessment time points into study days, assuming 1 month is equal to 30.4375 days. Middle points of scheduled assessments are determined.
- The time window associated with the previous assessment ends prior to the middle point; the time window associated with the latter assessment begins after the middle point. In case the middle point is an exact study day, it will belong to the previous assessment.
- The time window of first post-baseline assessment starts with Study Day 2, unless otherwise indicated.

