### **2.5.2 Statistical hypothesis, model, and method of analysis**

The primary analysis to address the primary objective will be based on the following estimand:

- Treatment of interest: Following a loading dose regimen consisting of once daily doses on days 1, 7 and 14, ofatumumab is given once monthly starting at Month 1. All doses of ofatumumab will be given subcutaneously via an auto injector at a dose of 20mg.
- Population: Relapsing MS participants currently treated with an infused aCD20 mAb, specifically ocrelizumab or rituximab, that have received at least 2 courses of therapy that are switching due to reasons other than safety or efficacy. Further defined through the appropriate inclusion/exclusion criteria to reflect the target population.
- Variable: Reduction or no change from baseline in the number of GdE lesions as observed by MRI (Yes, No).
- Other intercurrent events: Death or treatment/study discontinuation.
- Summary measure: Proportion of participants with no change or a reduction in the number of GdE T1 lesions at Month 12 and corresponding 95% confidence interval.

The 95% CI for the primary endpoint will be calculated using a normal approximation method. In addition, the change from baseline in the number of GdE T1 lesions will also be summarized descriptively by time point and graphically using a longitudinal plot.

Both non-responder imputation (NRI) for missing data and observed data approaches will be applied.

NRI is a conservative imputation method for dichotomous variables. NRI assumes that a participant is a treatment failure, i.e. non-responder, if they do not have a valid month 12 MRI assessment, or if they discontinue the study prematurely and do not have a valid month 12 MRI assessment. Hence, for missing data the primary variable outcome will be imputed to “No”. MRI assessments occurring after the efficacy cut-off will not be included in the analysis.

The primary analysis of the primary efficacy variable will be based on the FAS.

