### **2.5.4 Sensitivity analyses**

The primary analysis will be repeated to analyze no change or a reduction from baseline in the number of GdE T1 lesions observed by MRI at 12 months of treatment (Yes, No), based on observed data. MRI assessments occurring after the efficacy cut-off will not be included in the analysis.

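### SAP 2.4.2.2 and Table 2-4 conflict on whether an early discontinuer's exit MRI is a Month 12 value, which leaves the observed-data result and possibly the primary result open to either reading

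*SAP*

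**What the plan says.** **Collection.** Protocol Table 8-1, footnote 5: "EOS visit will be required for all participants (participants who permanently discontinue study drug and participants who complete the study". Footnote 11: "MRI scan at the EOS/EOT visit is required". Protocol Section 3 adds that for premature discontinuers "an End of Study visit must be performed within 7 days of study discontinuation". An exit scan can therefore fall on almost any study day.

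**Labelling.** SAP 2.4.2.2: "However, the final assessment of subjects who discontinue early is recorded as Month 12 (EOS".

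**Windows.** Table 2-4, which follows directly, has two post-baseline rows: Month 6 on Days 139-229 and Month 12 (EOS) on Days 321-427. The general rule in SAP 2.4.2 is that "visit windows are created to cover the complete range of days within the study", and "When visit windows are used, all visits will be re-aligned, i.e., they will be mapped into one of the visit windows".

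**Analysis.** SAP 2.5.2 applies both NRI and observed data. For NRI: "NRI assumes that a participant is a treatment failure, i.e. non-responder, if they do not have a valid month 12 MRI assessment". The SAP text does not define 'valid'. SAP 2.5.4 repeats the analysis "based on observed data. MRI assessments occurring after the efficacy cut-off will not be included in the analysis". SAP 2.5.4.1 repeats both approaches with assessments after the efficacy cut-off let in. It relaxes the cut-off (30.4375 days after the last dose, SAP 2.1.1.8) but not the windows.

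**The concern.** The same scan is called Month 12 by one rule and refused as Month 12 by the next, and the SAP does not rank them. Two programmers could follow the text faithfully and produce different numbers.

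If the window prevails, the observed-data analyses describe only people with a scan from about Month 11 onward. A participant whose required, centrally read, on-treatment exit scan showed more enhancing lesions than baseline leaves both numerator and denominator. This is the only sensitivity analysis set against NRI, and it omits documented failures of the endpoint itself. NRI in turn merges MRI breakthrough with discontinuation without MRI activity. No planned summary separates the two.

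If the label prevails, the problem moves to the primary analysis: a clean scan taken after a few weeks could be scored as efficacy maintained at Month 12.

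**Working it through.** **1. The plan's own figure.** SAP Section 3 gives half-widths of 8.5%, 7.8% and 7.0% for N = 100 at 75%, 80% and 85%. From 1.96 × √(p(1-p)/100) I get 8.49%, 7.84% and 7.00%. These reproduce, and this point does not affect them.

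**2. Days without an MRI window.** Days 2-138 are 137 days and Days 230-320 are 91 days, so 228 of the 319 days from Day 2 to Day 320 (71%) have no window. The other 91 (Days 139-229) map to Month 6. Exits on Days 321-351, before the general Month 12 window of Table 2-1 opens on Day 352, do fit the Month 12 MRI window. These are shares of days, not of participants. By contrast, Table 2-3 maps laboratory and questionnaire data continuously over Days 2-427.

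**3. Effect on the estimates.** Let p be the response proportion in completers, d the share exiting before Day 321, and q the share of exit scans showing an increase. Assume every completer has a Month 12 scan and every discontinuer an exit scan before the cut-off.

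- Observed data, Table 2-4 governs: p
- Counting exit scans: (1-d)p + d(1-q)
- Difference (observed minus counting exit scans): d(p - (1-q)), positive only when q > 1-p
- NRI, Table 2-4 governs: (1-d)p
- NRI, exit scan counted as Month 12: (1-d)p + d(1-q), which is higher by d(1-q)

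The documents state neither d nor q. With assumed d = 10%, and p = 85% (the highest of the plan's three proportions):

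| q (assumed) | Observed, Table 2-4 governs | Counting exit scans | Difference | NRI, Table 2-4 governs | NRI, exit scan counts |
|---|---|---|---|---|---|
| 0% | 85.0% | 86.5% | -1.5 | 76.5% | 86.5% |
| 5% | 85.0% | 86.0% | -1.0 | 76.5% | 86.0% |
| 25% | 85.0% | 84.0% | +1.0 | 76.5% | 84.0% |
| 50% | 85.0% | 81.5% | +3.5 | 76.5% | 81.5% |
| 100% | 85.0% | 76.5% | +8.5 | 76.5% | 76.5% |

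Over p = 75-85%, d = 5-20% and q = 0-100%, the observed-data difference runs from 0.20 × (0.75 - 1) = -5.0 to 0.20 × 0.85 = +17.0 points. The gap between the two NRI readings, d(1-q), runs from 0 to 20 points.

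**4. A worked case (assumed counts).** Take 100 participants, 15 early exits, and 2 failures among 85 completers. Observed data give 83/85 = 97.6% whatever the exit scans show. Counting exit scans:

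- no exit failures: 98/100 = 98.0%, so observed data are 0.4 points too low
- 3 exit failures: (83+12)/100 = 95.0%, so 2.6 points too high
- 5 exit failures: (83+10)/100 = 93.0%, so 4.6 points too high

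With 3 exit failures, NRI is 83.0% if Table 2-4 governs and 95.0% if the exit scan counts as Month 12.

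**The case against.** The best defence is that the narrow window is deliberate. Table 2-4 labels the row Month 11-13, and the endpoint is defined at Month 12. The sentence on early discontinuers may be there to explain why a window is needed, so that a Day 60 scan carrying a Month 12 label does not count. SAP 2.4.2 also allows different windows for assessments collected less often. This is the more natural reading, and the fix adopts it. The text does not say it, however. NRI in SAP 2.5.2 fails premature discontinuers who lack a valid Month 12 MRI, which implies that some have one.

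A reader might infer that the observed-data result overstates maintained efficacy. The documents do not support that. Clean exit scans are dropped too, and the sign depends on q against 1-p. Upward bias is plausible, since Protocol 6.1.4 lists disease progression as a reason to stop. But the only nearby figure is 4.6% with contrast-enhancing lesions on rituximab (Protocol 4.5), from a different setting. Applied to the worked case it gives 15 × 0.046 = 0.69 exit failures, or (83+14.31)/100 = 97.3%, a gap of 0.3 points. Adding only the known exit failures (83/88 = 94.3%) is not a fair comparator, because it leaves out the 12 clean exit scans.

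Other points stand as limits. If Table 2-4 governs, NRI is not inflated by this route. Exits on Days 139-229 keep a Month 6 value. The SAP rule on multiple assessments puts all results in listings, so the scans are not hidden. No hypothesis is tested. Exit scans are not assured: Protocol 9.1.2 makes the final evaluation subject to the participant's agreement, and Protocol 8.3.1 bars MRI during steroid treatment and for 30 days afterwards.

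Replacing the observed Month 12 analysis with a last-scan analysis would change a 12-month endpoint. That objection is sound, so the last-scan run belongs beside the planned analysis, not in its place.

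**Conclusion.** The conflict is real and should be resolved. SAP 2.4.2.2 and Table 2-4 give different answers for an exit scan before Day 321, and 228 of those 319 days have no MRI window despite the full-coverage rule in SAP 2.4.2.

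If Table 2-4 governs, the observed-data runs in 2.5.2, 2.5.4 and 2.5.4.1 omit these participants whatever their scan showed. The result can be too high or too low: -1.5 to +8.5 points at p = 85% and d = 10%, and -5.0 to +17.0 over the wider assumed range, whose extremes need every exit scan to be clean or every one to fail. If the label governs, the primary NRI proportion is higher by d(1-q), for example 9.5 points at d = 10% and q = 5%.

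All sizes rest on assumed d and q and on complete exit scanning. A claim that efficacy is overstated, or that 71% of discontinuers are lost, goes beyond the documents.

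**What to change.** Keep NRI as the primary analysis and the observed Month 12 analysis as planned. Then:

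1. In SAP 2.5.2, state that a valid Month 12 MRI must fall on Days 321-427, so earlier exit scans are not Month 12 values. Amend the sentence in 2.4.2.2 to match.
2. Add to Table 2-4 a row such as 'EOS - early discontinuation' for exit scans before Day 321.
3. Add to SAP 2.5.4.1 a supplementary run on the last on-treatment scan: the Month 12 scan or, for early discontinuers, the exit scan on or before the efficacy cut-off. Label it as such.
4. Tabulate the reasons for 'No' under NRI: increase at Month 12, increase at exit scan, exit scan without increase, no scan.

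The cost is SAP wording, one window row, one extra run and one table. The scans are already required and centrally read. The drawback is that exit scans reflect less than 12 months of treatment and not every discontinuer will have one, so the added run should report how many scans it uses and when they were taken.

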**Table 2-4 Visit windows for morphology**

Analysis Visit	Time Point	Scheduled visit day (study days)	Visit window (study days)
Baseline	-28 days	-28	-28 to 1
Visit 9	Month 5 - 7	184	139 to 229
(EOS) Visit 15	Month 11 – 13	366	321 to 427

#### **2.4.2.3 Treatment exposure and Electrocardiogram (ECG)**

Treatment exposure and ECG data will be presented according to the visit schedule, no visit windows will be applied.

#### **Multiple assessments**

It is possible that multiple assessments of a patient fall into the same visit-window (e.g., due to unscheduled visits). All results (scheduled and unscheduled) will be displayed in listings, but only one value (observed or derived) will be selected for summary statistics by visit-window.

For quantitative variables, the assessment closest to the target day will be selected. If more than one assessment is at the same distance to the target day, the later one will be selected.

For tables displaying the worst case scenario, such as shift tables or notable abnormalities, all assessments within a visit window will be used to identify the worst (e.g. the maximum or the minimum depending on parameter).

- **Baseline:** The last non-missing measurement made prior to or on the date of administration of the first dose of study treatment (the reference start date / Day 1). Only date part is considered if just one assessment on Day 1. If there are multiple assessments on Day 1, the following rules will apply:
  - a. If assessment time exists,
    - select the last available measurement prior to reference start date/time considering time;
  - b. If assessment time does not exist, select the available measurement from the lowest CRF visit number.
- **Post-baseline:** The measurement closest to the target day will be used. In the event two measurements are taken equally apart (e.g., 1 day before target date and 1 day after), the later one will be used. Cases where the same parameter is recorded more than once on the same date will be handled as follows:
  - a. If time of completion exists, the latest measurement will be used;
  - b. If time does not exist, the measurement from the lowest CRF visit number will be used.

In case categorical variables are based on continuous variables, the visit will be assigned to the continuous variable, and this visit will be used for the derived categorical variable.

